10.1 Neurocognitive Evaluation

10.1.1 Hopkins Verbal Learning Test (HVLT-R)

The HVLT-R incorporates 6 different forms, helping to mitigate practice effects of repeated administrations. Each form includes 12 nouns (targets) for memorization with 4 words drawn from 3 semantic categories, which differ across the 6 forms. Patients will be asked to recall from the list of 12 targets for 3 consecutive trials (immediate recall), identify the 12 targets from a list of semantically related or unrelated items (immediate recognition), and recall the 12 targets after a 20-minute delay (delayed recall). Raw scores will be derived for total recall, delayed recall, retention (percentage retained), and a recognition discrimination index. Each patient will serve as his/her own control, as the difference in scores obtained at baseline and at pre-specified post-treatment intervals will be calculated. The HVLT-R is owned and copyright protected by Psychological Assessment Resources, Inc. (PAR). Electronic distribution of the HVLT form is not currently permitted by PAR; please send an email to the study PI, [name], University of Maryland, to request a paper copy of the HVLT prior to enrolling any patients (or to get information regarding procuring institutional copies for the study). Future updates regarding electronic handling of these forms if allowed will be provided directly to the study teams, as and when available. Based on the copyright agreement with PAR, completed HVLT-R forms can be uploaded to NCI's secure, password protected online portal, iMedidata RAVE ("web portal"). The uploaded forms should contain the original copyright notice on the form. Access to the web portal shall be limited to authorized study personnel at the study site. Completed HVLT-R forms shall not be printed or downloaded from the web portal. Once uploaded to iMedidata RAVE, a hard copy of the completed HVLT-R forms should be mailed to the study PI.

Study personnel administering the HVLT must be previously credentialed in performing neurocognitive testing through existing mechanisms within cooperative groups including but not limited to participation in a prior NRG or Alliance or any other cooperative group study. Email a copy of this certification to the study PI, [name]. The PI may also approve other measures as applicable including but not limited to credentialing through training arranged by the study PI (or representative) or participating site's internal training. Each participating site should review the credentialing process with the study PI (or representative) prior to site activation. This requirement is necessary before any patients can be enrolled into the study at the site; see Site Registration, section 4.2.2. These assessments can be performed at an outside institution if appropriate research staff (credentialed and registered as a study team member prior to the evaluations) is available to complete adverse event and neurocognitive evaluation.

Scoring of HVLT-R

1. HVLT-R Delayed Recall

Patient scores on the HVLT-R delayed recall section have an integer range from 0 to 12 with lower scores indicating declining cognitive function. The score is the number of words a patient can recall from a list of 12 words. The change in score

from baseline to 2-, 4- and 6- months ranges from - 12 to 12. Change scores from 1 to 12 indicate declining cognitive function. A change score of 0 indicates preserved cognitive function. Change scores from -1 to -12 indicate improved cognitive function and are not expected.

2. HVLT-R Free Recall

Patient scores on the HVLT-R free recall section have an integer range from 0 to 36 with lower scores indicating declining cognitive function. The score is the number of words a patient can recall from a list of 12 words in three trials.

3. HVLT-R Delayed Recognition

10.1.2 Patient scores on the HVLT-R delayed recognition section have an integer range from -12 to 12 with lower scores indicating declining cognitive function. The score is the number of correctly identified words from the list of 12 words minus the number of incorrectly identified words from the list of 12 words.

10.2 Functional Assessment of Cancer Therapy with Brain Subscale (FACT-BR) for Quality of Life (QOL)

The FACT-BR is a multidimensional, self-report QOL instrument specifically designed and validated for use with brain malignancy patients. It is written at the 4th grade reading level and can be completed in 5 to 10 minutes with little or no assistance in patients who are not neurologically incapacitated. It measures quality of life related to symptoms or problems across 5 scales: physical well-being (7 items); social/family well-being (7 items); emotional well-being (6 items); functional well-being (7 items); and concerns relevant to patients with brain tumors (23 items). Items are rated on a five-point scale: 0-“not at all”, 1- “a little bit”, 2-“somewhat”, 3-“quite a bit” and 4-“very much”. The measure yields information about total QOL, as well as information about the dimensions of physical well-being, social/family well-being, emotional well-being, functional well-being, and disease-specific concerns. Six additional experimental items request information regarding how much each dimension affects QOL, using a "0" (not at all) to "10" (very much so) rating scale. Patient scores on the FACT-Br range from 0 to 92 with lower scores indicating declining quality of life. FACT-BR is self-administered and does not require precertification. It has been translated into 26 languages and is available free of charge to institutions with the completion of an agreement to share data, accessible at: <http://www.facit.org/facitorg/questionnaires>.

The assessments will be scored centrally by a blinded reviewer to avoid potential bias. The self-report of quality of life can be completed by the patient or the examiner and does not require pre-certification.

Scoring of FACT-BR Assessments:

The change scores from pretreatment from baseline to 2, 4 and 6 months will be estimated. A mean difference of 5 points represents a clinically meaningful change (CMC). A difference of less than 5 will not be considered meaningful, even if it has statistical significance.

11. MEASUREMENT OF EFFECT

Although the clinical benefit of IPdR has not yet been established, the intent of offering this treatment is to provide a possible therapeutic benefit, and thus the patients in part 2 of the study (to exclude patients treated at lower doses in part 1 thereby minimizing heterogeneity in response) will be carefully monitored for tumor response in addition to safety and tolerability. Patients with measurable disease will be assessed by standard criteria noted below. Each eligible patient must have at least one measurable lesion that will be included in the radiation treatment volume. If the measurable disease is restricted to a solitary lesion, the presence of malignancy must be confirmed by cytology/histology. Tumor lesion(s) included within the high dose radiation treatment volume ($\geq 95\%$ isodose line) will be considered as the target lesions for response evaluation. Patients with measurable disease will be assessed by standard criteria. For the purposes of this study, patients should be evaluated at baseline at 6 months (± 2 weeks) from the completion of WBRT. As guided by institutional practices, MRIs are also recommended during follow-up visits every 2 months (± 1 week) for the first 6 months and every 3-4 months (± 2 weeks) for the next 6 months from the completion of WBRT.

11.1 Antitumor Effect – Intracranial Metastases

Response and progression will be evaluated in this study using the new international criteria proposed by the revised Response Evaluation Criteria in Solid Tumors (RECIST) guideline (version 1.1) [*Eur J Ca* 45:228-247, 2009]. Changes in the largest diameter (unidimensional measurement) of the tumor lesions and the shortest diameter in the case of malignant lymph nodes are used in the RECIST criteria.

11.1.1 Definitions

Evaluable for toxicity. All patients will be evaluable for toxicity from the time of their first treatment with IPdR.

Evaluable for objective response. All patients will be evaluable for objective response from the time of their first treatment with IPdR.

Evaluable Non-Target Disease Response. Patients who have lesions present at baseline that are evaluable but do not meet the definitions of measurable disease, have received at least 7 daily doses of IPdR and have had their disease re-evaluated will be considered evaluable for non-target disease. The response assessment is based on the presence, absence, or unequivocal progression of the lesions.

11.1.2 Disease Parameters

Measurable disease. Measurable lesions are defined as those that can be accurately measured in at least one dimension (longest diameter to be recorded) as ≥ 10 mm (≥ 1 cm) with MRI. All tumor measurements must be recorded in millimeters (or decimal fractions of centimeters).

Non-measurable disease. All other lesions including small lesions (longest diameter <10 mm [< 1 cm]) are considered non-measurable disease.

Target lesions. All measurable lesions up to a maximum of 5 lesions in total should be identified as **target lesions** and recorded and measured at baseline. Target lesions should be selected on the basis of their size (lesions with the longest diameter) and should be those that lend themselves to reproducible repeated measurements. It may be the case that, on occasion, the largest lesion does not lend itself to reproducible measurement in which circumstance the next largest lesion which can be measured reproducibly should be selected. A sum of the longest diameters for all target lesions will be calculated and reported as the baseline sum diameters. The baseline sum diameters will be used as reference to further characterize any objective tumor regression in the measurable dimension of the disease.

Non-target lesions. All other lesions including any measurable lesions over and above the 5 target lesions should be identified as **non-target lesions** and should also be recorded at baseline. Measurements of these lesions are not required, but the presence, absence, or in rare cases unequivocal progression of each should be noted throughout follow-up.

11.1.3 Methods for Evaluation of Measurable Disease

All measurements should be taken and recorded in metric notation using a ruler or calipers. All baseline evaluations should be performed as closely as possible to the beginning of treatment and never more than 4 weeks before the beginning of the treatment.

The same method of assessment and the same technique should be used to characterize each identified and reported lesion at baseline and during follow-up.

Conventional MRI. MRI-scan based response evaluation is based on the assumption that MRI slice thickness is 5 mm (0.5 cm) or less. If MRI scans have slice thickness greater than 5 mm (0.5 cm), the minimum size for a measurable lesion should be twice the slice thickness. It is recommended that MRI sequences be followed per the consensus recommendations as detailed in the article: “Consensus recommendations for standardized brain tumor imaging protocol in clinical trials. Benjamin M. Ellingson *et al.* Neuro Oncol. 2015 Sep; 17(9):1188-98. doi: 10.1093/neuonc/nov095. Epub 2015 Aug 5.”

Please contact the PI and the Radiology Co-Investigators, [name], [name] or [name], with any questions.

11.1.4 Response Criteria

11.1.4.1 Evaluation of Target Lesions

Complete Response (CR): Disappearance of all target lesions.

Partial Response (PR): At least a 30% decrease in the sum of the diameters of target lesions, taking as reference the baseline sum diameters.

Progressive Disease (PD): At least a 20% increase in the sum of the diameters of target lesions, taking as reference the smallest sum on study (this includes the baseline sum if that is the smallest on study). In addition to the relative increase of 20%, the sum must also demonstrate an absolute increase of at least 5 mm (0.5 cm). (Note: the appearance of one or more new lesions is also considered progressions).

Stable Disease (SD): Neither sufficient shrinkage to qualify for PR nor sufficient increase to qualify for PD, taking as reference the smallest sum diameters while on study.

11.1.4.2 Evaluation of Non-Target Lesions

Complete Response (CR): Disappearance of all non-target lesions and normalization of tumor marker level.

Non-CR/Non-PD: Persistence of one or more non-target lesion(s) and/or maintenance of tumor marker level above the normal limits.

Progressive Disease (PD): Appearance of one or more new lesions and/or *unequivocal progression* of existing non-target lesions. *Unequivocal progression* should not normally trump target lesion status. It must be representative of overall disease status change, not a single lesion increase.

Although a clear progression of “non-target” lesions only is exceptional, the opinion of the treating physician should prevail in such circumstances, and the progression status should be confirmed at a later time by the review panel (or Principal Investigator).

11.1.4.3 Evaluation of Best Overall Response

The best overall response is the best response recorded from the start of the treatment until disease progression/recurrence (taking as reference for progressive disease the smallest measurements recorded since the treatment started). The patient's best response assignment will depend on the achievement of measurement criteria.

For Patients with Measurable Disease (i.e., Target Disease)

Target Lesions	Non-Target Lesions	New Lesions	Overall Response
CR	CR	No	CR
CR	Non-CR/ Non-PD	No	PR
CR	Not evaluated	No	PR
PR	Non-CR/ Non-PD/ Not evaluated	No	PR
SD	Non-CR/ Non-PD/ Not evaluated	No	SD
PD	Any	Yes or No	PD
Any	PD*	Yes or No	PD
Any	Any	Yes	PD

For Patients with Non-Measurable Disease (i.e., Non-Target Disease)

Non-Target Lesions	New Lesions	Overall Response
CR	No	CR
Non-CR/non-PD	No	Non-CR/non-PD*
Not all evaluated	No	not evaluated
Unequivocal PD	Yes or No	PD
Any	Yes	PD

* ‘Non-CR/non-PD’ is preferred over ‘stable disease’ for non-target disease since SD is increasingly used as an endpoint for assessment of efficacy in some trials so to assign this category when no lesions can be measured is not advised

11.1.5 Duration of Response

Duration of overall response: The duration of overall response is measured from the time measurement criteria are met for CR or PR (whichever is first recorded) until the first date that recurrent or progressive disease is objectively documented (taking as reference for progressive disease the smallest measurements recorded since the treatment started).

The duration of overall CR is measured from the time measurement criteria are first met for CR until the first date that progressive disease is objectively documented.

Duration of stable disease: Stable disease is measured from the start of the treatment

until the criteria for progression are met, taking as reference the smallest measurements recorded since the treatment started, including the baseline measurements.

11.1.6 Intracranial Progression-Free Survival

The date at which intracranial progression is radiographically identified will be used to calculate the intracranial PFS. Intracranial PFS will be measured from the date of start of treatment to time of progression or death, whichever occurs first. Intracranial PFS will be assessed 2, 4, 6 and 8 months after the initiation of study therapy. If intracranial progressive disease is seen on MRI, any subsequent MRI scans will be performed as clinically indicated standard of care.

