NCI-Supplied Agent: 5-iodo-2-pyrimidinone-2'-deoxyribose (IPdR; NSC # 726188)

IND Sponsor: DCTD, NCI.

Protocol Type / Version # / Version Date:

Original / Version 1 / December 15, 2015
Resubmission / Version 2 / February 11, 2016
Resubmission / Version 3 / March 22, 2016
Resubmission / Version 4 / April 1, 2016
Resubmission / Version 5 / April 19, 2016
Resubmission / Version 6 / June 27, 2016
Resubmission / Version 7 / September 21, 2016
Resubmission / Version 8 / October 26, 2016
Resubmission / Version 9 / November 3, 2016
CTSU Activation on December 7, 2016
Amendment 1 / FDA Response / Version 10 / January 6, 2017
Amendment 2 / Version 11 / January 19, 2017
Amendment 3 / Version 12 / July 26, 2017
Amendment 4 / Version 13 / October 2, 2017
Amendment 5 / Version 14 / October 23, 2017
Amendment 6 / Version 15 / December 12, 2017
Amendment 6 / Version 15 / April 3, 2018
Amendment 6 / Version 16 / May 3, 2018
Amendment 7 / Version 17 / February 5, 2020
Amendment 8 / Version 18 / July 7, 2020
Amendment 9 / Version 19 / September 4, 2020

SCHEMA

	Pre-study	Week 1 Days 1-7	Week 2 Days 8-14	Week 3 Days 15-21	Week 4 Days 22-28	Week 5 Days 29-35
IPdR				po qd dose x 28 days, days 1-28	→	
RT				2.5 Gy/fraction x 15 fractions days 8-12, 15-19, 22-26	→	

PROTOCOL SYNOPSIS

Title	Phase 1 and Pharmacology Study of Oral 5-iodo-2-pyrimidinone-2-deoxyribose (IPdR) as a Prodrug for IUDR-Mediated Tumor Radiosensitization in Brain Metastases

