5.5 Duration of Follow Up

Patients will be evaluated for up to two years from the study registration or until death, whichever occurs first. From the date of completion of WBRT, follow-ups would be done through clinic visits every 2 months (\pm 1 week) for the first 6 months, every 3-4 months (\pm 2 weeks) for the next 6 months and every 6 months (\pm 3 weeks) for the next one year. After the first DLT assessment visit (primary endpoint), these visits in the first 6 months can be performed at an outside institution if appropriate research staff (credentialed and registered as a study team member) is available to complete adverse event and neurocognitive evaluation. After the first 6 months of follow up, clinic visits may be replaced by phone calls or visits at an outside institution, if not felt feasible for logistic reasons. Follow up notes or documentation of phone calls must be included in the study chart. Patients removed from study for unacceptable adverse event(s) will be followed until resolution or stabilization of the adverse event.

Follow-up MRI at 6 months (\pm 2 weeks) from the completion of WBRT is required to assess intracranial treatment response and disease control. As guided by institutional practices, MRIs are also recommended to be performed during follow-up visits every 2 months (\pm 1 week) for the first 6 months and every 3-4 months (\pm 2 weeks) for the next 6 months from the completion of WBRT.

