- e. On Days 15 and 22 of the 28-day dosing schedule, blood will be obtained just prior to the po drug administration and then at 30, 60, 120 and 240 minutes following po dosing. A five minute positive or negative margin on each of the above times on Day 1 (30 through 240 minutes) is acceptable.
- f. %IUDR-DNA cellular incorporation. Sample collection will be prior to study (Day 1) and at Days 8, 15, 22 and 29 of the 28-day treatment followed by first two-month follow up.
- g. Follow-up MRI at 6 months (\pm 2 week) from the completion of WBRT is required. As guided by institutional practices, MRIs are also recommended during follow-up visits every 2 months (\pm 1 week) for the first 6 months and every 3-4 months (\pm 2 weeks) for the next 6 months from the completion of WBRT. If progressive disease is seen on MRI, subsequent evaluations are not required for study.
- h. For patients accrued to part 2 of the study, please send anonymized pre- and post-treatment (up to 6 months from the date of completion of WBRT) scans via FTP or hard copy CD to the study PI for central review of response.
- i. From the date of completion of WBRT, follow-up visits to be done every 2 months (\pm 1 week) for the first 6 months, then and are recommended every 3-4 months (\pm 2 weeks) for the next 6 months then every 6 months (\pm 3 weeks) for the next one year. These visits can be performed at an outside institution if appropriate research staff (credentialed and registered as a study team member prior to the evaluations) is available to complete adverse event, neurocognitive testing and QOL evaluation. After the first 6 months of follow up, clinic visits may be replaced by phone calls or visits at an outside institution. Follow up notes or documentation of phone calls must be included in the study chart.
- j. Neurocognitive and quality of life evaluation to be performed at the D35 assessment time-point and then during follow-up visits every 2 months (\pm 1 week) for the first 6 months from the date of completion of WBRT (for patients without intracranial progression). A total of 5 neurocognitive and quality of life evaluations will be performed: Baseline, D35, 2-, 4- and 6- months from the date of completion of WBRT.
- k. To be performed only if feasible if the patient is removed from the study.
- l. Perform biopsy only if patient has an easily accessible tumor.
- R. Research.

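### The 6-month intracranial PFS estimate is read before the only required follow-up MRI, and Section 11.1.6 counts time from a different origin than the MRI calendar

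*Combined protocol and SAP*

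**What the plan says.** Six-month intracranial PFS is a secondary objective (Section 1.2.2). Four rules determine its value.

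- **Origin and dating (11.1.6).** "Intracranial PFS will be measured from the date of start of treatment to time of progression or death, whichever occurs first". Also: "The date at which intracranial progression is radiographically identified will be used to calculate the intracranial PFS".
- **Assessment times (11.1.6).** "Intracranial PFS will be assessed 2, 4, 6 and 8 months after the initiation of study therapy".
- **Analysis (13.4.4).** The Kaplan-Meier estimate at 6 months is reported with its standard error. Progression and death are events. Living patients without progression are censored at their last imaging date.
- **Imaging (5.5; Section 10 note g; Section 11).** One follow-up MRI is mandatory, at 6 months plus or minus 2 weeks "from the completion of WBRT is required to assess intracranial treatment response and disease control". The others are optional. In 5.5, "MRIs are also recommended to be performed during follow-up visits every 2 months"; in note g, "As guided by institutional practices, MRIs are also recommended during follow-up visits every 2 months". All are counted from the end of WBRT. The off-study MRI is done only where feasible (Section 10 note k).

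The Schema fixes the radiotherapy days: "2.5 Gy/fraction x 15 fractions days 8-12, 15-19, 22-26".

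**The concern.** The endpoint clock starts on Day 1, while the imaging clock starts when WBRT ends, almost four weeks later. A 6-month figure on the first clock is read before the required 6-month scan on the second. A progression before month 6 that no optional scan catches, in a patient still alive at month 6, is dated after the landmark and does not count. In the other direction, a living patient lost before any follow-up scan is censored at baseline, while observed deaths count. The result therefore depends on how often sites choose to scan and on who is lost, and the reported standard error shows neither. No section maps the 2, 4, 6 and 8 month assessments of 11.1.6 onto the MRI calendar.

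**Working it through.** **1. Schedule check.** Three blocks of 5 days give 15 fractions; 15 x 2.5 Gy = 37.5 Gy, as the plan states. The last fraction is on Day 26, which is 25 days after Day 1.

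**2. When the scans fall, in months from Day 1** (30.44 days per month). 25/30.44 = 0.82 and 14/30.44 = 0.46.

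- Required MRI: 0.82 + 6 = 6.82, plus or minus 0.46, so 6.36 to 7.28.
- With the 14-day hold allowed in Section 6: 6.82 to 7.74.
- Recommended scans: 2.82 and 4.82 (with the 1-week window, 2.59 to 3.05 and 4.59 to 5.05).

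By calendar date, the required window opens 8 to 14 days after the 6-month anniversary for every start date in a year.

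**3. What follows without a model.** With the required MRI only, no unscheduled scan and full follow-up, no progression can be dated by month 6. Only deaths are events, so the estimate equals 6-month overall survival.

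**4. Size with no loss.** The plan gives no expected rate, so these inputs are assumptions:

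- Death and progression are independent and exponential.
- Median survival is 7.1 months (Section 2.1, best prognostic class), so OS(6) = 2^(-6/7.1) = 0.557.
- Progression by month 6 is p = 1 - 0.85^0.5 = 7.8%, from the 85% control at 12 months quoted in Section 2.1 for a more selected population. Rates of 15% and 30% are assumed for range.

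The error is OS(6) x p with the required MRI only, and OS(6) x [exp(-4.82L) - exp(-6L)], L = -ln(1-p)/6, with all recommended scans.

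| Progression by month 6 | Required MRI only | Recommended scans done |
|---|---|---|
| 8% | +4.3 points | +0.8 |
| 15% | +8.4 | +1.5 |
| 30% | +16.7 | +2.8 |

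**5. What shrinks these figures.** If progression multiplies the death hazard by 2, 3 or 5 (assumed), the required-MRI-only error at 8% falls to 3.3, 2.5 or 1.7. At median survival 2.3 months (worst class), the first column becomes 1.3, 2.5 and 4.9. Scans prompted by symptoms shrink the error further.

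**6. What reverses them.** I simulated 1,000,000 patients at median survival 7.1, with leaving times uniform before the required MRI and deaths after leaving unknown. With the required MRI only and 8% progression, the net error is about +0.9 at 20% loss, near zero at 24% and -4.0 at 40%. With the recommended scans done and 20% to 40% loss, it lies between about -1.9 and +1.9 across the three progression rates.

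**7. Scale.** True 6-month intracranial PFS at 8% progression is 0.557 x 0.922 = 0.513. With 19 to 25 patients (Section 13.2), sqrt(0.513 x 0.487/n) gives 11.5 to 10.0 points.

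**The case against.** The strongest reply is that the worst case is unlikely. It needs every patient to go unscanned for six months, although 11.1.6 plans assessments, 5.5 recommends an MRI at two-monthly visits, and symptoms would prompt imaging. With the recommended scans the error is 0.8 points at the only rate derived from the documents, far below the standard error. This stands, and it limits the size of the point. It does not remove the mismatch: 11.1.6 does not require an MRI at its assessment times, and three sections make the interim scans optional.

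Three stronger readings do not hold.

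- A reader might infer that 6-month intracranial PFS will be overstated. Late dating pushes it up, but censoring the lost at their last scan can push it down by as much or more.
- A reader might infer that the 6-month estimate should be replaced by a proportion at the required MRI. That changes the stated endpoint. With the recommended scans and 20% to 40% loss, the proportion is also further from its own target (about -2.7 to -7.6 points) than the current rule is from its target (about -1.9 to +1.9).
- A reader might see a further conflict in Section 10 note j, which schedules neurocognitive tests "for the first 6 months from the date of completion of WBRT (for patients without intracranial progression"). That reads naturally as no known progression, so it adds nothing here.

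**Conclusion.** The point holds as a minor one. The dates follow from the plan alone: the required MRI always comes after the 6-month landmark, and two time origins are in use. As written, the plan does not deliver the progression part of a 6-month estimate without optional scans. The percentage errors rest on assumed exponential times, an assumed link between progression and death, and a progression rate borrowed from another population; they show scale, not a forecast. No test, threshold or dose decision depends on this endpoint. What is at stake is how the figure can be read, especially if later studies use it as a reference.

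**What to change.** 1. Reconcile the assessment times in 11.1.6 with the MRI calendar in 5.5, Section 10 and Section 11, so that the endpoint, its landmark and the required MRI share one time origin.
2. In 13.4.4, keep the 6-month Kaplan-Meier estimate. State that its progression component depends on optional scans, and report how many patients were scanned before month 6 and the scan dates.
3. As a supplementary analysis only, report the proportion alive and free of intracranial progression at the required MRI, labelled as about 7 months from start. Count deaths and earlier progressions as failures. Leave living patients with no such MRI and no earlier progression out of the proportion, and give their number. Add an exact binomial confidence interval (for example, 9 of 25 is 36%, 18.0% to 57.5%) and bounds counting the missing patients all as failures and all as successes.

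The cost is wording and a small table, with no extra scans; the censoring rule already needs the imaging dates. The supplementary figure has its own weakness. In the simulations it is biased downward by about 2 to 3 points at 20% loss and 5 to 8 at 40%, or about 4 to 5 at 20% loss if deaths after leaving are counted. It also still depends slightly on optional scans, because these decide whether a patient who later misses the required MRI is a failure or is left out.
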